7.1.5 Software

All analyses will be conducted using SAS[®] Version 9.4 (or above).

8. Statistical considerations

8.1.1 Sample size

With the high titre RV3-BB neonatal vaccine schedule as the active control arm, the sample size is calculated to demonstrate the non-inferiority of the lower titre vaccine arms with respect to the proportion of participants who have a serum IgA response, 4 weeks after 3 doses of vaccine. A non-inferiority margin of 20% for the difference between arms will be used.

The primary analysis is based on the per protocol population defined as participants who receive all 3 doses of RV3-BB and have no major protocol violations. Thirty percent of participants are expected to be excluded from the PP population due to death, study withdrawal, loss to follow-up, or study non-compliance. Among those in the PP population, a 50% response probability is assumed for the active controls. Based on a one-sided 0.025 level score test with 90% power under the alternative of no difference in response probabilities, 172 participants per arm are required for a total sample size of 688 participants.

8.1.2 *Multicentre studies*

Approximately 688 babies will be randomised across three sites in Malawi. Study visits will be conducted at the sites or at participant homes.

8.1.3 Missing data

Where possible, data from participants who withdraw prematurely from the study will be included in any analysis.

Participants with missing baseline IgA measurements will be assigned a value below the lower limit of detection (i.e assigned a value of 10) in the calculation of serum immune response (although the cord blood IgA value will still be acknowledged as missing when summarising titre). Partial date imputation of adverse events and concomitant medications are mentioned in respective sections.

9. Primary and Secondary Analyses

In order to be included in the analysis of cumulative vaccine take, participants must have at least one of IgA response or shedding data following any dose of IP

Where:

- 1. An IgA response is defined as a 3-fold rise from baseline, where baseline is defined as cord blood for neonatal comparison and post dose 1 blood for infant comparison (or cord if post dose 1 data is missing). It will be assumed that cord blood is 10 if cord blood is missing).
- 2. Shedding data is defined as having stool data for at least 1 time point from days 3-5 post vaccine.

All available data on IgA response, shedding at all time points (post dose 1, 2 and 3 for the neonatal comparison and post doses 2, 3 and 4 for the infant comparison) will be used to determine whether vaccine take is positive or negative for each individual, with participants classified as having a positive vaccine take if any response (IgA, or shedding days 3-5) at any time point is positive, and classified as negative for vaccine take otherwise (i.e. if all known measurements at all time points are negative).

9.1.1 Variables and derivations

Primary endpoint:

A serum IgA response in the *neonatal* schedule, is defined as $a \ge 3$ -fold increase from baseline, where baseline is defined as stated in sections 7.1.2 and 8.1.3 for handling of missing baseline IgA measurements of this analysis plan.

Secondary endpoints:

- A serum IgA response in the *infant* schedule, is defined as a ≥ 3-fold increase from baseline, where baseline is defined as stated in sections 7.1.2 and 8.1.3 for handling of missing baseline IgA measurements of this analysis plan.
- Cumulative vaccine take is defined as vaccine take observed at the current assessment time point or following any previous dose, where vaccine take is

defined as \geq 3-fold increase in serum anti-rotavirus IgA from baseline to post IP dosing, or detectable RV3 shedding in stools (by ELISA or PCR) any day from day 3 to 5 following administration of IP.

- Shedding of RV3-BB is defined as presence of RV3-BB shedding in stool from days 3-5 following each dose of IP.
- Geometric mean titre of the anti-rotavirus serum IgA response after 3 doses of RV3-BB.
- Safety and tolerability (as per sections 15 to 16 of this analysis plan) of RV3-BB.
- Occurrence of diarrhoea episodes in participants, according to severity and detection of wild-type rotavirus.

Derivations:

A participant will, at each vaccine titre, be defined a "responder" if he/she has a serum *IgA response* (\geq 3-fold increase in serum anti-rotavirus IgA from baseline) for neonatal arms IP dose 1 - 3 and infant arm IP dose 2 - 4 of RV3-BB. The response rate will be dichotomised (0 = non-responder, 1 = responder).

Geometric means (and associated summary statistics) will be determined as follows:

- 1. Log-transform the titre data (if not already log-transformed)
- 2. Determine the arithmetic mean and other descriptive statistics of the transformed data using the PROC MEANS procedure
- Exponentiate the output obtained from the PROC MEANS procedure, depending on data to be presented (log-transfer vs not log-transformed)
- 9.1.2 Analysis

Non-inferiority of lower titre vaccines (primary as well as secondary endpoints):

The difference between high and low titre arms in the response rate and its 95% confidence interval will be calculated. The cumulative probability of anti-rotavirus serum IgA response (as defined above) by 18 weeks of age will be estimated by the Kaplan-Meier method for each vaccine arm. PROC LIFETEST (SAS[®] Version 9.4 or above) will

be used to analyse the response rates (non-responder *vs.* responder). With the CENSOR variable, 1 is commonly used to indicate that an event occurred (subject is a responder) and 0 indicates that the event did not occur (the subject was censored/is a non-responder).

Non-inferiority of the lower titre vaccine will be demonstrated if the upper bound of the confidence interval is below 20%.

Additionally, we will calculate the 95% CI of the difference between vaccine groups in the serum IgA response rate after dose 3 using the method of Newcombe-Wilson without continuity correction for the difference between binomial proportions as implemented in PROC FREQ (SAS® Version 9.4 or above).

Generalized estimating equations (GEE) will be used to analyse the response rates (non-responder vs. responder) after dose 3 using PROC GEE (SAS® Version 9.4 or above). We will calculate a binary outcome ($1 = \ge 3$ -fold increase, 0 = < 3-fold increase from baseline) after dose 1, 2, and 3 for each participant who received vaccine according to the neonatal schedule. After that, we will fit a model with dose as a discrete/categorical/factor variable, vaccine group (low, medium, high dose) as a discrete variable, and dose by vaccine group interaction term. The model will use the binomial distribution for the outcome variable and the exchangeable correlation matrix to account for the correlation between a participant who received vaccine according to the neonatal schedule outcomes. Model will be used for the analysis. Once the model is fit, contrast statements will be used in PROC GENMOD (SAS® Version 9.4 or above) to calculate the difference in the response rate after dose 3 for the high versus low dose and so forth.

In the table, (Estimate, standard error, 95% CI) will be presented.

The general linear model to be fit by GEE is

 $logit(p_{ij}) = \beta_{ij}$

where p_{ij} is the response rate after the i-th dose in the j-th vaccine group. Differences between the β s represent the log odds ratio in response rates.

MCRI-RV3-BB-004

The cumulative vaccine take and the components of vaccine take (i.e. secondary endpoints) will be estimated similarly,

All summary and listing of immunogenicity data will be based on the FAS, ITT and PP populations. All the primary endpoint, primary sensitivity and secondary endpoint efficacy analysis will be based on the PP and ITT populations.

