13.3 Data Analysis Considerations

All immunogenicity and safety data will be listed and summarised using descriptive statistics by treatment group and nominal time. The descriptive summary for the categorical variables will include counts and percentages. The descriptive summary for the continuous variables will include means, medians, standard deviations and minimum and maximum values. Where possible, data from participants who withdraw prematurely from the study will be included in any analysis. Further details on the handling of withdrawals and/or missing data will be specified in the SAP.

All statements of statistical significance will be based on a two-sided test at the 5% level of significance, unless stated otherwise. Further details will be specified in the SAP.

The baseline value for each clinic assessment will be the last pre dose value obtained.

Full details of the statistical analyses will be presented in the SAP. Any deviations from the planned analyses detailed in the protocol will be documented in the SAP and final study report. If the study is prematurely discontinued, all available data will be listed and a review will be carried out to determine which statistical analyses are considered appropriate.

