13.3.2 Immunogenicity Analyses

13.3.2.1 Definition of baseline IgA for the calculation of vaccine take

Due to the timing of the blood tests, baselines for serum anti-rotavirus IgA are defined differently for participants in the neonatal vaccine schedule and the infant vaccine schedule. Baseline serum anti-rotavirus IgA in the neonatal vaccine schedule is defined as the measurement from the cord blood. In the infant vaccine schedule baseline is defined as the measurement from analysis of serum collected prior to the second dose, although the measurement from the cord blood may be used if there are no data on IgA following the first dose of IP.

Further details of the analysis of secondary endpoints will be described in the SAP. Details about multiplicity and Type I error for secondary endpoints will be included in the SAP.

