7.1.4 Statistical tests

A single analysis will be performed at the end of the trial. No interim analyses are planned.

Primary Analysis:

The primary analysis and primary sensitivity analysis are based on the per protocol population defined as participants who receive all 3 doses of RV3-BB and have no major protocol violations (after reviewed and agreed at the end of the study). Thirty percent of participants are expected to be excluded from the PP population due to death, study withdrawal, loss to follow-up, or study non-compliance.

Non-inferiority of the lower titre vaccine will also be assessed in the intention to treat population. The cumulative probability of response by 18 weeks of age will be estimated by the Kaplan-Meier method for each vaccine arm. The difference between high and low titre arms in the cumulative probabilities and its 95% confidence interval will be calculated. If the upper bound of the confidence interval is below 20%, non-inferiority of the lower titre vaccine will be demonstrated.

Additionally, we will calculate the 95% CI of the binomial proportions using the method of Newcombe-Wilson without continuity correction and generalized estimating equations (GEE) after dose 3 on the PP and ITT analyses set.

All the primary and primary sensitivity analysis will be based on PP and ITT analysis set.

See section 10 for additional details.

Secondary Analyses:

Immunogenicity and vaccine-take results will be (inferentially) analysed as done for the primary analysis. Descriptive analyses are described in section 10.

Safety

No formal statistical testing will be performed on the safety data.

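### The SAP carries the 20-point non-inferiority rule to vaccine take and its components at unadjusted alpha, and omits the secondary multiplicity details that the protocol deferred to it

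*SAP*

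**What the plan says.** **The rule and its reach.** SAP 9.1.2 is headed "Non-inferiority of lower titre vaccines (primary as well as secondary endpoints". Beneath that heading: "Non-inferiority of the lower titre vaccine will be demonstrated if the upper bound of the confidence interval is below 20"%. The section ends with "The cumulative vaccine take and the components of vaccine take (i.e. secondary endpoints) will be estimated similarly". SAP 7.1.4, under secondary analyses, agrees: "Immunogenicity and vaccine-take results will be (inferentially) analysed as done for the primary analysis".

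**The level.** An upper two-sided 95% bound is a one-sided 0.025 test. That matches the design statement in SAP 8.1.1: "Based on a one-sided 0.025 level score test with 90% power under the alternative of no difference in response probabilities". Protocol 13.3 gives the general default: "All statements of statistical significance will be based on a two-sided test at the 5% level of significance, unless stated otherwise". Neither document states a different level for secondary endpoints.

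**The deferred detail.** Protocol 13.3.2.1: "Details about multiplicity and Type I error for secondary endpoints will be included in the SAP". The SAP supplied has no alpha split, hierarchy or gatekeeping, and does not say that secondary comparisons are unadjusted. SAP section 5, on changes from the planned analysis, does not mention the omission.

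**Text pointing the other way.** SAP 9.1.4 (IgA response by time point), 9.1.6 and 9.1.7 (take after two doses and after one) and 9.1.8 (shedding) specify frequency tabulations. SAP 9.1.5 (take after three doses) defines a positive result but has no such wording.

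**The margin.** SAP 8.1.1 and Protocol 13.1 state the 20-point margin for serum IgA response after three doses, where "a 50% response probability is assumed for the active controls".

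**The concern.** Read as written, the SAP lets each secondary titre comparison end in a statement that non-inferiority has been demonstrated, each at full alpha and with no statement of how many such comparisons there are. The trial exists to decide whether a lower titre is good enough (Protocol 3.9). A titre that failed the IgA primary could still be reported as non-inferior on vaccine take, under the SAP's own rule.

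A second problem is separate from multiplicity. A margin set beside an assumed 50% response rate is carried unchanged to an endpoint that may run much higher. Protocol 3.8.3 reports cumulative take of 78/83 (94%) for the neonatal schedule in the earlier efficacy trial.

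**Working it through.** **1. The plan's own figure, for the evaluable number.** With 50% in both arms, margin 0.20, one-sided 0.025 and 90% power, the simple unpooled formula gives

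n = (1.960 + 1.282)² × (0.25 + 0.25) / 0.20² = 131.3, so 132 evaluable per arm.

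132 × 1.3 = 171.6, so 172, which is the stated figure. (Dividing by 0.7 instead would give 189; that is a different point.) With the stated 30% exclusion, 172 × 0.7 = 120 evaluable per arm, which is used below.

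**2. How many tests?** The SAP gives no count. Two readings bracket it:
- Narrow: take and shedding after three doses, two lower titres: 2 × 2 = 4 tests.
- Wide: take, shedding and IgA response after one, two and three doses, less the primary, two lower titres: (9 − 1) × 2 = 16 tests.

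**3. Chance of at least one false call.** The condition is that every compared endpoint at both titres is truly exactly 20 points worse. If all tests were independent:
- 4 tests: 1 − 0.975⁴ = 9.6%
- 16 tests: 1 − 0.975¹⁶ = 33.3%

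The tests are not independent, because both titres share the high-titre control and the endpoints overlap. Take a normal statistic Z = (X − C)/√2 for each endpoint and titre. C is shared by the two titres, the correlation ρ applies across endpoints within an arm, and a false call is any Z > 1.960. Simulation gives:

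| ρ between endpoints | 4 tests | 16 tests |
|---|---|---|
| 0 | 8.9% | 31.1% |
| 0.3 | 8.4% | 25.4% |
| 0.5 | 8.1% | 21.1% |
| 0.7 | 7.5% | 16.2% |
| 0.9 | 6.3% | 10.3% |

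The documents do not give ρ. A participant-level simulation used 120 per arm, Newcombe bounds, take defined as either component, and assumed rates with the components exactly at the margin and take at or beyond it. It gave 14-17% for 16 tests and 6-7% for 4.

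**4. What the margin does on take.** Exact binomial enumeration, 120 per arm, proportion of trials with the Newcombe upper bound below 20 points:

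| High titre vs lower titre | Declared non-inferior |
|---|---|
| 50% vs 40% | 37% |
| 75% vs 65% | 42% |
| 94% vs 84% | 68% |
| 94% vs 80% | 29% |
| 94% vs 74% (at the margin) | 2.7% |

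The same 10-point deficit passes 68% of the time at 94% and 37% at 50%. At 94% vs 84%, the proportion without take rises from 6% to 16%.

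**The case against.** **The tabulation sections show that the secondaries are descriptive.** This has weight. Several of the 16 comparisons are specified only as tabulations, and SAP 9.1.2 ties the Newcombe interval and the GEE contrast to the time after dose 3. The narrow family is therefore at least as natural as the wide one. It does not remove the problem: 9.1.5 has no tabulation wording, and 7.1.4 and 9.1.2 place take under the inferential rule. SAP 7.1.4 sends the reader to section 10 for the descriptive analyses, but section 10 covers participant disposition. The SAP disagrees with itself and needs the edit either way.

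**The error rate is being exaggerated.** A reader might infer from the 16-test row that about one trial in five will make a false secondary claim. The documents do not support that. The figure needs all 16 comparisons to be formal tests, ρ near 0.5, and a deficit of exactly 20 points on every endpoint at both titres. With only one titre at the margin (8 tests), it is 12.6% at ρ = 0.5. Deficits beyond the margin give a smaller error. Take contains the other two measures and accumulates over doses, so high correlation is plausible.

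**The 68% is not an error.** Correct. A 10-point deficit lies inside a 20-point margin, so declaring non-inferiority obeys the rule, and at the margin the rate is nominal. The figure bears only on whether 20 points suits this endpoint. The 94% is also borrowed from a trial in Indonesia at 8.3 × 10⁶ FFU/mL. At 75% vs 65% the rate falls to 42%.

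**The protocol did not promise adjustment.** Also correct. It promised details, and a plain statement that no adjustment is made would have met that.

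**Conclusion.** The concern stands in this form. The SAP applies a stated non-inferiority rule to take and its components at an unadjusted one-sided 0.025, is inconsistent about which secondaries it covers, and gives none of the multiplicity detail the protocol assigned to it. This is more than missing text, because following the rule as written would produce non-inferiority claims with no error control behind them.

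The family-wise error at the margin is about 6-9% on the narrow reading and 10-31% on the wide one (33% under full independence), against 2.5% per test. These figures depend on the assumed family, the assumed correlation, and true deficits of exactly 20 points throughout. The textual defect depends on none of them.

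Separately, the 20-point margin has no stated basis for take and would be permissive if control take were near 94%, which is an assumption. The primary comparison is not affected by either point.

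**What to change.** 1. SAP 9.1.2: remove from the heading the bracketed words that extend it to secondary endpoints, and state that the 20-point rule applies only to the primary serum IgA endpoint.
2. SAP 7.1.4: replace the sentence that analyses secondaries inferentially as for the primary. State that all secondary contrasts, including neonatal versus infant schedule and first dose versus placebo, are reported as differences with nominal 95% intervals, are descriptive and unadjusted for multiplicity, and carry no non-inferiority conclusion. Correct the pointer to section 10.
3. SAP 9.1.2, closing sentence on take and its components: say that the same interval methods are used for estimation, without the decision rule. This brings it into line with 9.1.4 and 9.1.6 to 9.1.8.

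The cost is SAP wording only, with no new data or tables. The sponsor gives up formal non-inferiority statements on secondary endpoints. If it wants to keep some, the SAP should list them, justify a margin for each, and control the error, either by a fixed sequence after the primary or by splitting alpha (0.025/4 = 0.00625 for four tests, 0.025/16 = 0.0016 for sixteen).

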3.6.1 Advantages of the birth dose strategy

Rotavirus infection often occurs very early in life, particularly in developing countries. In Africa, 38% of hospitalisation due to rotavirus infection occurs in infants less than 6 months of age (Cunliffe, 1998). The rotavirus seropositivity rate among placebo recipients 1 month after the last dose had been given in a trial of Rotarix® was greater among Malawian infants than among South African infants (40.4% vs 16.7%) suggesting that Malawian infants have high exposure to wild-type rotavirus infection in the first 5 months of life (Cunliffe et al., 2012). The current vaccines administered from 6 weeks of age, with completion of a 2- or 3-dose course at 4–6 months may be too late to protect some infants. Neonatal vaccine administration offers the earliest possible protection.

Providing a rotavirus vaccine at birth has the potential to address sub-optimal efficacy of rotavirus vaccination in high burden countries and improve safety concerns. It also may increase the proportion of infants living in remote regions completing a full course of a rotavirus vaccine.

Birth dose administration may limit interference to vaccine take, as most newborns have a neutral gastric environment and minimal breast milk intake. The intestinal microbiota is not yet well established and intussusception is rare (Dennehy et al., 2007). Based on the unique structural and functional characteristics of neonatal rotavirus strains, it is proposed that RV3-BB is an ideal vaccine for a birth dose strategy. Natural infection with RV3 is associated with replication without symptoms but provides heterotypic protection against severe rotavirus disease for the first 3 years of life (Bishop et al., 1983). A birth dose of a rotavirus vaccine may also be safer as the natural intussusception risk is lowest in the neonatal period.

Neonatal rotavirus strains replicate well in the immature newborn intestine despite the presence of maternal and breast milk antibodies. They generally cause asymptomatic infections, but induce a protective immune response against rotavirus on re-infection (Bishop et al., 1983). The RV3-BB rotavirus vaccine based on a neonatal rotavirus strain may be the ideal candidate for a birth dose vaccine strategy.

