4 STUDY OBJECTIVES

4.1 Primary Objective

The primary objective is to assess the cumulative anti-rotavirus serum IgA response (defined as a \geq 3 fold increase from baseline) 4 weeks after 3 doses of RV3-BB administered in a neonatal schedule at a vaccine titre of 1x10⁷, 3 x 10⁶ or 1 x 10⁶.

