10.5 Doses and treatment regimens

Approximately 688 participants will be prospectively randomised to one of the following four treatment groups in a 1:1:1:1 ratio.

- High dose neonatal RV3-BB vaccine schedule (1x10⁷titre dose). RV3-BB Vaccine for doses 1, 2 and 3 and placebo for dose 4
- Mid dose neonatal RV3-BB vaccine schedule (3x10⁶titre dose). RV3-BB Vaccine for doses 1, 2 and 3 and placebo for dose 4.
- Low dose neonatal RV3-BB vaccine schedule (1x10⁶titre dose). RV3-BB Vaccine for doses 1, 2 and 3 and placebo for dose 4.
- High dose Infant RV3-BB vaccine schedule (1x10⁷titre dose). Placebo for dose 1 and RV3-BB Vaccine for doses 2, 3 and 4

Participants will also receive a dose of commercially available Rotarix® at 18 weeks of age.

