13.1 Sample Size Assumptions

With the high titre RV3-BB neonatal vaccine schedule as the active control arm, the sample size is calculated to demonstrate the non-inferiority of the lower titre vaccine arms with respect to the proportion of participants who have a serum IgA response 4 weeks after 3 doses of vaccine. A non-inferiority margin of 20% for the difference between arms will be used. The primary analysis is based on the per protocol population defined as participants who receive all 3 doses and have no major protocol violations. Thirty percent of participants

are expected to be excluded from the PP population due to death, study withdrawal, loss to follow-up, or study non-compliance. Among those in the PP population, a 50% response probability is assumed for the active controls. Based on a one-sided 0.025 level score test with 90% power under the alternative of no difference in response probabilities, 172 participants per arm are required for a total sample size of 688 participants.

Non-inferiority of the lower titre vaccine will also be assessed in the intention to treat population. The cumulative probability of response by 18 weeks of age will be estimated by the Kaplan-Meier method for each vaccine arm. The difference between high and low titre arms in the cumulative probabilities and its 95% confidence interval will be calculated. If the upper bound of the confidence interval is below 20%, non-inferiority of the lower titre vaccine will be demonstrated.

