6.1.4 Per-protocol (PP) Analysis Dataset

All participants from the ITT population who completed the study in compliance with the protocol and who reported no major violation of the study protocol which may have effect on the primary endpoint. Participants will be analysed according to the treatment to which they were randomised. Primary analyses will be performed on the PP set.

7. General considerations

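### The neonatal primary endpoint is the week-14 sample, but the SAP's only non-inferiority rule follows a Kaplan-Meier estimate at 18 weeks, and the deciding confidence interval is not named

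*SAP*

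**What the plan says.** **Endpoint.** Protocol 4.1 sets the primary objective as IgA response "4 weeks after 3 doses of RV3-BB administered in a neonatal schedule at a vaccine titre of" 1×10⁷, 3×10⁶ or 1×10⁶. Protocol 10.5 gives the neonatal arms "RV3-BB Vaccine for doses 1, 2 and 3 and placebo for dose 4". SAP 20.1.16 places IP dose 3 at Visit 5 (week 10) and IP dose 4 at Visit 7 (week 14). It labels the week-18 visit as post IP dose 4.

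**Responder definition.** SAP 9.1.1 defines a responder by a ≥3-fold rise "for neonatal arms IP dose 1 - 3 and infant arm IP dose 2 - 4 of RV3-BB".

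**Analysis.** SAP 9.1.2, under a line covering primary and secondary endpoints, opens with the response-rate difference and its 95% CI. It then states: "The cumulative probability of anti-rotavirus serum IgA response (as defined above) by 18 weeks of age will be estimated by the Kaplan-Meier method". The rule that the upper bound must be below 20% comes after that. Protocol 13.1 has "The cumulative probability of response by 18 weeks of age will be estimated by the Kaplan-Meier method for each" arm, and SAP 7.1.4 has equivalent text; both attach it to the ITT assessment. SAP 9.1.2 adds a Newcombe-Wilson interval and a GEE model for response after dose 3, without a decision rule for either.

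**Per-protocol set.** SAP 6.1.4 takes "All participants from the ITT population who completed the study in compliance with the protocol". SAP 7.1.4 takes "participants who receive all 3 doses of RV3-BB and have no major protocol violations".

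**The concern.** For the neonatal arms, week 18 is eight weeks after the last vaccine dose and four weeks after a placebo dose. It is four weeks after the third RV3-BB dose only in the infant arm. A Kaplan-Meier estimate at 18 weeks can therefore count neonatal responses that arise after the endpoint sample.

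Such late responses would come largely from wild-type infection. Protocol 3.6.1 reports 40.4% seropositivity among Malawian placebo recipients in an earlier vaccine trial, "suggesting that Malawian infants have high exposure to wild-type rotavirus infection in the first 5 months of life". New infection that adds responders to every arm at the same rate among non-responders pulls the arms together. In a non-inferiority comparison that makes a false claim for a lower titre more likely.

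The per-protocol set has the same anchoring problem. SAP 10.1.1 defines completion as attending all trial visits. A neonatal infant with a valid Visit 7 sample but no Visit 9 is then out under 6.1.4 and in under 7.1.4.

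**Working it through.** **1. The plan's own figure.** Inputs from SAP 8.1.1: margin 0.20, control response 0.50, no true difference, one-sided 0.025, power 90%, 30% excluded from the per-protocol set.

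n = (1.960 + 1.282)² × (0.25 + 0.25) / 0.20² = 131.3, so 132 per arm. Then 132 × 1.30 = 171.6, so 172, as stated. With 30% excluded, 172 × 0.70 ≈ 120 per arm, the per-protocol size used below. (Dividing 132 by 0.70 would give 189; that is a separate matter.)

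**2. Which sample is the endpoint.** Third RV3-BB dose at week 10, plus 4 weeks, is week 14: the Visit 7 blood, drawn before IP dose 4. The Visit 9 blood is drawn before Rotarix, so Rotarix adds no responses. Infection before week 14 is part of the endpoint on any reading.

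**3. Effect of counting week 18.** Let q be the share of week-14 non-responders who newly respond by week 18, equal in all arms.

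- p18 = p14 + (1 − p14) × q
- difference at week 18 = (1 − q) × difference at week 14

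Example with q = 10%: 0.50 + 0.50 × 0.10 = 0.55 and 0.30 + 0.70 × 0.10 = 0.37, a gap of 18.0 points. The 20-point margin at week 18 then corresponds to 0.20 / 0.90 = 22.2 points at week 14.

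**4. A plausible range for q.** The documents give no week 14 to 18 rate. If the 40.4% accrued at a constant hazard over T weeks, q = 1 − (1 − 0.404)^(4/T): 12.1% for T = 16, 9.8% for T = 20 and 9.0% for T = 22. T is assumed, and seropositivity stands in for a new 3-fold rise.

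**5. False non-inferiority.** True week-14 response is 50% versus 30%, exactly at the margin. The rule is an upper 95% bound below 20%, evaluated by exact binomial enumeration. With no censoring, Kaplan-Meier with Greenwood variance equals the Wald interval.

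| q | Week-18 response | Gap (points) | Wald, 120 per arm | Score, 120 per arm | Wald, 172 per arm |
|---|---|---|---|---|---|
| 0 | 50.0% vs 30.0% | 20.0 | 2.5% | 2.6% | 2.3% |
| 5% | 52.5% vs 33.5% | 19.0 | 3.5% | 3.9% | 3.7% |
| 10% | 55.0% vs 37.0% | 18.0 | 4.6% | 5.6% | 5.6% |
| 15% | 57.5% vs 40.5% | 17.0 | 6.1% | 7.7% | 8.2% |

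The 172 column is the upper limit for an ITT analysis. The q = 0 row is also the result when neonatal events stop at Visit 7.

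**The case against.** The strongest reply is that the SAP already excludes the week-18 sample. The Kaplan-Meier sentence refers back to the definition above it. That definition stops at IP dose 3 for neonatal arms, and SAP 9 and 9.1.5 likewise confine the neonatal comparison to doses 1 to 3. On that reading the neonatal curve is flat after week 14 and there is no dilution. This stands as a possible reading, but it is not settled. SAP 9.1.1 names no visit or cut-off, week-18 blood is also after doses 1 to 3, and an 18-week time point would then serve no purpose in these arms.

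Second, Protocol 13.1 and SAP 7.1.4 attach the Kaplan-Meier rule to the ITT set, which SAP 6.1.3 calls supportive. That also stands. But SAP 9.1.2 covers the primary endpoint, 7.1.4 and 9.1.2 run the primary analyses on both PP and ITT, and no other rule is given.

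A reader might infer three stronger things that the documents do not support:

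- **That the powered endpoint is never analysed.** The dose-3 proportion is analysed by Newcombe-Wilson and GEE. What is missing is a statement that one of these decides.
- **That using actual visit days badly inflates the curve.** SAP 9.1.2 does not define the time variable. In simulations with 120 per arm, visits spread over their windows and assumed week-18 response of 55% versus 37%, reading the curve at day 126 gave about 53% versus 34% and non-inferiority in about 3% to 4% of trials. Readings near 64% for the high titre, with non-inferiority in about 7% to 10%, arose only beyond 18 weeks, which the SAP does not call for.
- **That neonatal arms get four assessments against three in the infant arm.** SAP 9.1.5 gives each schedule three post-dose assessments for vaccine take, and the stated 20% rule compares titres.

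On the per-protocol set, exclusions are settled at a blinded review, and no bias between neonatal arms is shown. The two definitions still differ.

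**Conclusion.** The time points conflict, and the interval that decides the per-protocol primary analysis is not named. Both can be settled from the documents' own endpoint definition.

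The statistical consequence is conditional and modest. If week-18 samples count, the nominal 2.5% error becomes about 3.5% to 6.1% (Wald) or 3.9% to 7.7% (score) for q between 5% and 15% at 120 per arm. If only samples after doses 1 to 3 count, it stays nominal. The figures assume q is equal across arms, no censoring, and a true difference exactly at the margin. Late vaccine-driven responses or unequal infection would change them. This should be fixed before analysis, but it does not undermine the design.

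**What to change.** 1. In SAP 9.1.2, state that the non-inferiority decision is the per-protocol difference, high minus lower titre, in the proportion with a ≥3-fold rise at any sample up to Visit 7. Compare the upper 95% bound with 20%, using the Newcombe-Wilson interval already planned or the score interval that matches the sample-size basis. Name one.
2. Read any Kaplan-Meier estimate at Visit 7 for the neonatal arms and at Visit 9 for the infant arm, with nominal visit as the time variable. Report neonatal Visit 9 IgA descriptively. Align SAP 7.1.4, and record the departure from Protocol 13.1 in SAP section 5.
3. Reconcile SAP 6.1.4 with 7.1.4 so that a neonatal infant with a valid Visit 7 sample is not dropped from the per-protocol set for later events.

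The cost is SAP wording and one changed time point in the programs. No new data are needed. The sample size is unaffected, because it already rests on response four weeks after dose 3.
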